10.2.2.5 Fat-soluble Vitamin Deficiency

Queries related to TEAEs indicative of end-organ damage, i.e., impaired hepatic synthetic function presenting as e.g., bone fracture/rickets, GI or other organ bleeding/ecchymosis or night blindness, will be issued when a patient presents with worsening of fat-soluble vitamin deficiency (see [Section 10.2.1](#) for monitoring fat-soluble vitamin levels by laboratory assessments). Treatment should be discontinued in patients with evidence of end-organ damage due to fat-soluble vitamin deficiency.

10.2.2.6 Treatment-emergent Iron Deficiency Anemia

Events of iron deficiency anemia are identified as part of TEAE reporting and hematology assessments. Patients will be evaluated for fecal blood loss if they present with:

- A decrease in hemoglobin of ≥ 2 g/dL
- A report of blood in stool; if so, a further diagnostic work up will be performed, following confirmation of blood in stool with hemoccult cards.

Patients will be managed per institutional standard of care with iron supplementation.

10.2.2.7 Re-challenge after Discontinuation/Interruption of Study Drug

The DSMB will evaluate the safety data for patients who have discontinued study drug for an extended period on a case-by-case basis to determine whether re-challenge with A4250 is appropriate. The minimal duration of the discontinuation should be at least one to two weeks.

Patients that have discontinued for an extended period and allowed re-challenge by DSMB will use the last labs prior to restart as the new baseline for determining if DILI criteria are met.

10.2.2.8 Monitoring after Permanent Discontinuation of Study Drug Due to Safety

Once study drug is permanently discontinued for liver, hepatitis, diarrhea, or other severe AE related to study drug, the patient will be monitored weekly until the laboratory and clinical parameters have normalized/stabilized.

10.2.3 Demographics/Medical and Surgical History (For Cohort 2 only)

Demographic information per country regulations, along with medical and surgical history, will be obtained and recorded in the eCRF at Visit S-1.

Medical and surgical history will be entered in the eCRF at Visit S-1. This includes date of diagnosis of PFIC, prior investigational medications for PFIC, historical (3 months prior to Screening, and up to 5 years prior to Screening for BRIC) hepatic biochemical parameters (e.g., AST, ALT, and total bilirubin), ongoing medication, any surgery performed, any other diagnosis, and historical biopsy data.

For patients with BRIC, information on flares will be collected, including frequency, duration, and severity of flares within the last 6 months at a minimum, and within the last 5 years, if possible. A flare/cholestatic episode can be self-reported or clinically assessed based on medical history. Clinical signs and symptoms during a cholestatic episode/flare can include nausea, vomiting and pruritus followed by jaundice, fatigue, weight loss, malaise, steatorrhea, night blindness. Increased bilirubin and alkaline phosphatase levels and increased INR can be observed. ALT, AST and GGT can be normal to mildly elevated.

If a liver biopsy has been performed within 1 year prior to Screening, or during the study, the results will be recorded in the eCRF.

10.2.4 Clinical Genetic Testing (For Cohort 2 only)

For previous confirmatory clinical genetic testing results for PFIC, including BRIC, Type performed prior to Screening Visit S-1, the confirmatory clinical genetic testing laboratory report will be verified to determine eligibility.

If the historical clinical genetic result is equivocal, unavailable, or unobtainable, clinical genetic analysis will be performed to confirm pathologic biallelic variations of the *ATP8B1*, *ABCB11* *ABCB4*, *NR1H4*, *TJP2*, *DCDC2*, *CLDN1*, and *MYO5B* genes and verified to determine eligibility. No other diagnostic genetic testing will be offered.

10.2.5 Physical Examination

A physician or suitably trained qualified assistant will perform a complete physical examination, including a skin examination, at Visits S-1, 1, 3, 5, 8, and 11.

A complete physical examination will include assessment of general appearance, eyes, ears, nose, throat, head/neck/thyroid, lymph nodes, cardiovascular, lungs/chest, abdomen, genitourinary, extremities, skin, musculoskeletal, neurologic, and other. An abbreviated

physical examination will include general appearance, cardiovascular, abdomen, and other assessments based on patient status.

Skin will be thoroughly examined and excoriations/scratch marks recorded.

10.2.6 Vital Signs

Evaluation of vital signs will be performed at all visits. This includes blood pressure (systolic and diastolic), pulse, respiratory rate, temperature, height/length (using certified stadiometer), mid-arm circumference (3 repeat measures), and body weight (using a certified weight scale) at clinic visits. BMI will be calculated.

10.2.7 Abdominal ultrasound

Ultrasound of the liver and spleen will be performed at Visits 1, 5, 8, and 11. Liver size, echogenicity, and presence of masses/nodules as well as spleen size will be recorded.

10.2.8 Overdose

A4250 is minimally absorbed and has a very low systemic availability. Based on toxicology data, for study purposes any dose exceeding a total of >3 mg/kg body weight of A4250 taken as a single dose or as a cumulative dose within 24 hours is defined as an overdose.

The no-adverse-effect dose level in the most sensitive species (defined as 20 mg/kg/day) in the rat 1 month toxicity study gives a human equivalent dose of approximately 194 mg/day in a 60 kg person. This dose is approximately 10-fold higher than the maximum possible dose predicted in human studies (20 mg).

The investigator/investigative staff should immediately, and not later than within 24 hours of knowledge, report an overdose in the SAE Report Form. In the event of an A4250 overdose, the patient should be monitored closely.

10.2.9 Pregnancy

If a pregnancy is discovered in a female patient enrolled in the study before the end of dosing the patient will be immediately discontinued from the study and will attend the same visits as a prematurely withdrawn patient. If the pregnancy is discovered after the end of dosing the patient will continue in the study per protocol. If a pregnancy occurs in a male patient's partner at any time during the study, the pregnancy should also be reported and followed.

Pregnancy is not considered to be an AE. However, if the patient has been dosed with the study drug, the pregnancy must be reported on the Paper Pregnancy Notification Form immediately within 24 hours after recognition to Pharmacovigilance Manager and Pharmacovigilance and Safety Services Department (please refer to [Section 10.1.3](#)). Date of exposure and as far as possible, details of the period of gestation at the time of exposure must be given.

The pregnancy should be followed up to determine outcome, including spontaneous termination, details of birth, and presence of any birth defects, congenital anomalies or

newborn or maternal complication. An infant who was exposed in-utero will be followed for up to 2 years after delivery. Individual cases with an abnormal outcome in association with the study drug should be reported on an expedited basis, i.e., reported rapidly to a competent authority.

11 STATISTICAL EVALUATION

11.1 Sample Size and Power

There is no formal hypothesis testing in this open label study. Sample size for Cohort 1 was determined in Study A4250-005. For Cohort 1, patients will be enrolled following completion or participation of 12 weeks of Study A4250-005. The expected proportion of patients with at least one event, i.e., surgical bile diversion or liver transplantation or death, in untreated patients is expected to be high enough to be able to detect an improvement after A4250 treatment. For the other endpoints, mainly descriptive analyses will be performed.

The proportion of patients with at least one event (i.e., surgical bile diversion or liver transplantation or death), that can be expected in a non-treated population depends on PFIC type and age distribution of the included patients. The expected proportion of patients with events will be calculated for the study population once each patient's age and PFIC type are known, using the probability that a patient will get an event estimated from the reference population in the ongoing observational cohort study, NAtural Course and Prognosis of PFIC and Effect of Biliary Diversion (NAPPED).

As an example, if the expected proportion with at least one event is estimated to be 30% in the study population, and then if the proportion of patients with at least one event during A4250 long-term treatment are shown to be only 10% in the study, the power is approximately 89% to 96% (1-sided test, alpha=2.5%) for a confidence interval (CI) with upper boundary <30% based on a sample size of n=48 to 60. The sample size of 60 patients for Cohort 2 was estimated based on the availability of target patient population to evaluate the therapeutic benefit for those patients.

11.2 Statistical Methods

11.2.1 Statistical Analysis Sets

Full Analysis Set

The full analysis set (FAS) will consist of all patients who received at least 1 dose of study drug in Study A4250-008. The FAS will be the primary analysis set for all analyses unless otherwise specified.

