7.2.1 Inclusion Criteria

Cohort 1:

1. Completion of the 24-week Treatment Period of Study A4250-005 or withdrawn from Study A4250-005 due to patient/caregiver judgment of intolerable symptoms after completing at least 12 weeks of treatment. Patients who withdraw from A4250-005 due to a study drug related AE will not be eligible.
2. Signed informed consent and assent as appropriate. Patients who turn 18 years of age (or legal age per country) during the study will be required to re-consent to remain on the study.
3. Patients expected to have a consistent caregiver for the duration of the study.
4. Caregivers (and age-appropriate patients) must be willing and able to use an eDiary device as required by the study.

Cohort 2:

1. A male or female patient of any age, with a clinical diagnosis of PFIC, including episodic forms (i.e., BRIC), and with a body weight ≥ 5 kg at Visit S-1.
2. Patient must have clinical genetic confirmation of PFIC.
3. Patients with PFIC, excluding BRIC, must have elevated serum bile acid concentration, specifically measured to be ≥ 100 $\mu\text{mol/L}$, taken as the average of 2 samples at least 7 days apart (Visits S-1 and S-2) prior to the Screening/Inclusion Visit (Visit 1).

4. Patients with PFIC, excluding BRIC, must have history of significant pruritus and a caregiver-reported observed scratching or patient-reported itching (for patients >18 with no caregiver-reported observed scratching) in the eDiary average of ≥ 2 (on 0 to 4 scale) in the 2 weeks prior to the Screening/Inclusion Visit (Visit 1).
5. Patients with episodic forms of PFIC (i.e., BRIC) must have an emerging flare characterized by clinically significant pruritus and elevated serum bile acid levels/cholestasis as judged by the investigator.
6. Patient and/or legal guardian must sign informed consent (and assent) as appropriate. Patients who turn 18 years of age (or legal age per country) during the study will be required to re-consent in order to remain in the study.
7. Age appropriate patients are expected to have a consistent caregiver for the duration of the study.
8. Caregivers and age-appropriate patients (≥ 8 years of age, if able) must be willing and able to use an eDiary device as required by the study.

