11.2.2.6 Evaluation of Secondary and Exploratory Efficacy Variables

All secondary and exploratory variables listed under [Sections 9.1.2](#) and [9.1.3](#) will be analyzed descriptively for categorical and continuous data, as applicable. For continuous data, the change from baseline will be analyzed in addition to the actual visit values. For categorical data, shift tables or frequency and percentages of patients will be presented as appropriate.

Change in growth (Z-score, SD from P50 standard growth curve) will be analyzed by using one-sample T-test or Wilcoxon signed-rank test as appropriate. Change in growth (height/length for age, weight for age, BMI, and mid-arm circumference) will also be displayed using graphical presentations.

A 95% CI will be calculated for the proportion of patients experiencing surgical bile diversion or liver transplantation or death as well as for the proportion of patients experiencing surgical bile diversion or death or liver transplantation. The upper boundary will be compared to the expected proportion of events, using the event probability estimated from the untreated reference population in an ongoing observational cohort study.

Time to first event, i.e., time to surgical bile diversion or liver transplantation or death, will be explored by descriptive statistics and Kaplan-Meier curves, which also will be used to make a comparison to the NAPPED population. The propensity score matched cohort analysis using inverse probability of treatment weights will be used to match the study patient population to the reference population based on age group and PFIC type.

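### The diversion, transplant or death comparison with the untreated reference counts only patients dosed in Study 008, so A4250-treated Study 005 patients who did not roll over are left out

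*Protocol*

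**What the plan says.** Section 11.2.1 defines the analysis set: "The full analysis set (FAS) will consist of all patients who received at least 1 dose of study drug in Study A4250-008". It then gives the scope: "The FAS will be the primary analysis set for all analyses unless otherwise specified".

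Section 11.2.2.6 plans a 95% confidence interval for the event proportion, whose upper limit is set against the proportion expected from an untreated observational cohort. It adds: "Time to first event, i.e., time to surgical bile diversion or liver transplantation or death, will be explored by descriptive statistics and Kaplan-Meier curves". The curves are also compared with that cohort, weighted on age group and PFIC type. No other analysis set is named, and no time origin is given.

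Under section 7.2.1, Cohort 1 patients must have completed 24 weeks of Study 005, or have left it for intolerable symptoms after at least 12 weeks. The same criterion adds: "Patients who withdraw from A4250-005 due to a study drug related AE will not be eligible". Section 7.2.2 also bars Cohort 1 patients who were non-compliant in Study 005 or who have decompensated liver disease.

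Section 11.1 gives a worked example for this endpoint with 30% expected and 10% observed, "based on a sample size of n=48 to 60", and a power of about 89% to 96%.

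**The concern.** A secondary objective (section 6.2) is the effect of A4250 on biliary diversion and transplantation. For children randomised to A4250 in Study 005, treatment began in Study 005. The planned set picks them up only after 12 to 24 weeks on drug, and only if they met the roll-over criteria. The untreated reference passes through no filter based on drug-related adverse events or compliance with this drug. This is prevalent-user selection: patients who fail early on treatment can drop out of view before counting starts.

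At stake is the interpretation of the one comparison for which the protocol quotes a power. An upper limit below the reference rate could partly reflect who was allowed to roll over.

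**Working it through.** **1. The plan's own figure.** Inputs from section 11.1: expected proportion 0.30, observed 0.10, n = 48 to 60, one-sided alpha 2.5%. The exact upper limit for x events in n is the 0.975 quantile of Beta(x+1, n−x). The criterion is met when that limit is below 0.30.

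- n = 48: at most 7 events (limit 0.278; 8 events give 0.302). P(X ≤ 7 | 48, 0.10) = 0.898 and P(X ≤ 7 | 48, 0.30) = 0.011.
- n = 60: at most 10 events (limit 0.285; 11 give 0.304). P(X ≤ 10 | 60, 0.10) = 0.966 and P(X ≤ 10 | 60, 0.30) = 0.014.

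The stated 89% to 96% is reproduced, so the power figure is not in error. The question is which patients the proportion describes.

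**2. Does the choice of time zero remove the selection?** The protocol does not state one, so take both candidates.

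- From Study 008 Day 1: continuing-A4250 children have already had 12 to 24 weeks on drug and have passed the filter.
- From Study 005 Day 1, with the same set: they are credited with 12 to 24 weeks during which they could not have died, since a death would have kept them out of the set.

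Neither origin removes the selection while the set is limited to patients dosed in Study 008.

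**3. What selection alone could do.** Assume no drug effect and a true risk among selected children below the 30% benchmark. The size of the reduction is an assumption. The chance of meeting the criterion is P(X ≤ 7 | 48, p) or P(X ≤ 10 | 60, p):

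| True risk p | n = 48 | n = 60 |
|---|---|---|
| 0.30 | 0.011 | 0.014 |
| 0.275 | 0.027 | 0.037 |
| 0.25 | 0.061 | 0.086 |
| 0.20 | 0.229 | 0.323 |

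**4. Can the size be fixed by adding omitted patients back?** The protocol does not give their number or their events. Assume 60 children in Study 005 allocated 1:1:1, of whom 48 roll over. Two thirds of the other 12, that is 8, then had A4250. Let the 48 have 10% events (4.8).

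- If 30% to 50% of the 8 had events: (4.8+2.4)/56 = 12.9% to (4.8+4)/56 = 15.7%. Against an unchanged 30% benchmark the chance of success is 82% to 62%, compared with 90% for the 48 alone.
- This adds Study 005 time to the treated side only. If 30% is taken as a 72-week risk at constant hazard, the 96-week risk is 1 − 0.7^(96/72) = 37.8%. With 40 A4250 children at 96 weeks and 16 placebo children at 72 weeks, the aligned benchmark is (40×0.378 + 16×0.30)/56 = 35.6%. The chances become 98% and 91%.
- If the 8 have only the 24-week untreated risk, 1 − 0.7^(24/72) = 11.2%, they add 0.9 events: 5.7/56 = 10.2%, essentially unchanged.

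The same trial can thus show a large loss, none, or hardly any change in the proportion, depending on inputs that the protocol does not contain.

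**The case against.** An analysis set of everyone dosed in the extension is ordinary for an extension study. The protocol states that there is no formal hypothesis testing, the endpoint is secondary, and time to event is only explored. Section 11.2.2.1 already presents placebo-to-A4250 children separately and pools them with Cohort 2 excluding BRIC, a group with no A4250 before Study 008. Section 11.1 computes the expected proportion from each included patient's age and PFIC type. If age at Study 008 entry is used, being event-free up to entry is partly handled. All of this stands and limits the weight of the point. It does not remove selection on drug-related withdrawal, compliance or decompensation.

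Three stronger readings are tempting but unsupported:

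- A reader might infer that the event clock starts at Study 008. Baseline 2 in section 11.2.2.1 defines a value, not a time origin, and the SAP may set the origin.
- A reader might infer that everyone who rolls over tolerated or did well on the drug. Section 7.2.1 admits some who left Study 005 for intolerable symptoms, and non-responders who completed 24 weeks also qualify. Nor do the Cohort 1 exclusions name diversion, so a diverted child is not shown to be excluded.
- A reader might infer a loss of power to 82% or 62%. The 30% is only an example with no stated duration, the other inputs are invented, and the loss disappears once the benchmark covers the same follow-up.

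**Conclusion.** The point holds as a selection problem of unknown size. By default, the event proportion and Kaplan-Meier comparison leave out A4250-treated Study 005 patients who died or otherwise did not roll over. Weighting on age group and PFIC type cannot restore them. The result for continuing-A4250 patients can therefore favour A4250. Patients on placebo in Study 005 and Cohort 2 are not affected by selection on earlier A4250 exposure.

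The table in the working shows only how sensitive the criterion is to an assumed shift in risk; it does not estimate the bias. The conclusion rests on the default set applying to this endpoint, since no exception is written. It does not require the Study 008 set to be replaced as the main analysis; that would be a debatable preference.

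**What to change.** - Keep the Study 008 full analysis set for the event analyses and state its time zero.
- Add a supportive event-proportion and time-to-first-event analysis from the first A4250 dose in either study: Study 005 Day 1 for children randomised to A4250 there, Study 008 Day 1 for all others. Include every A4250-treated Study 005 patient whether or not they rolled over, and censor those who did not at last contact.
- Align the reference cohort's start and length of follow-up with that analysis.
- Report the event comparison separately for patients with no A4250 before Study 008, using the grouping already in section 11.2.2.1 (Study 005 placebo plus Cohort 2 excluding BRIC).

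The cost is protocol or SAP wording and linkage to the completed Study 005 data. Cohort 1 patients keep their Study 005 numbers (section 8.6), which makes linkage straightforward. No new patients or procedures are needed. The drawbacks are unequal follow-up, up to 96 against 72 weeks, which Kaplan-Meier methods accommodate, and a possibly less favourable estimate.

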11.2.2 Methods of Statistical Analyses

11.2.2.1 General Principles

Descriptive statistics will mainly be used in this open-label extension study. Patients with BRIC will be presented separately in efficacy assessments. All statistical analyses will be performed using SAS version 9.3 or higher.

Baseline 1 will be defined as the last value prior to treatment start in Study A4250-005 for Cohort 1 patients.

Baseline 2 will be defined as the last value prior to treatment start in Study A4250-008 for all patients. Baseline 2 will be used in all analyses unless otherwise specified.

Descriptive statistics will be summarized for Cohort 1, Cohort 2 excluding BRIC, Cohort 2 BRIC, and combined Cohort 1 + Cohort 2 excluding BRIC. Within Cohort 1, the following subgroups will be presented: ‘A4250 40 µg/kg/day (-005) to 120 µg/kg/day (-008)’, ‘A4250 120 µg/kg/day (-005) to 120 µg/kg/day (-008)’, ‘A4250 40 µg/kg/day (-005) and 120 µg/kg/day (-005) to 120 µg/kg/day (-008)’, and ‘placebo (-005) to 120 µg/kg/day (-008)’. Within Cohort 2 excluding BRIC, 3 subgroups (‘40 µg/kg/day’, ‘40 µg/kg/day to 120 µg/kg/day’, and ‘120 µg/kg/day’) will be presented. Cohort 1 Placebo to A4250 120 µg/kg/day will also be combined with Cohort 2 excluding BRIC for presentations.

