PFIC is life-threatening and debilitating. Other than odevixibat (A4250 non-proprietary name), which is approved for the treatment of PFIC by the European Medicines Agency (EMA) and for the treatment of pruritus in patients with PFIC by the United States Food and Drug Administration (US FDA), the therapeutic choices are restricted to non-specific therapy of the symptoms and signs of the disease such as nutritional support, preventing vitamin deficiencies, and treatment of extrahepatic features. Medical treatment options include off-label use of ursodeoxycholic acid, rifampin, antihistamines, and naltrexone. A minority of patients respond nominally and transiently to these interventions. Biliary diversion is used to decrease systemic

bile acids through interruption of the enterohepatic circulation and so avoid transplantation. Liver transplantation is typically only viewed as an option when patients have failed medical treatment and/or biliary diversion and have liver failure or persistent uncontrolled pruritus.

Previously, the term benign recurrent intrahepatic cholestasis (BRIC) was used to identify a group of patients with episodic cholestasis including severe pruritus and jaundice. Genetic analysis of patients with episodic cholestasis have identified mutations in the *ATP8B1* and *ABCB11* genes (the same mutations as PFIC1 and PFIC2). It is now generally recognised that, within each subtype, PFIC and BRIC represent 2 extremes of a continuous spectrum of phenotypes of the one disease [Bull 2018; Stapelbroek 2010; Sticova 2018].

Genetic diagnosis of BRIC Type 1 or BRIC Type 2 is based on evidence of mutations in both alleles of the corresponding genes. While the age of first manifestation can vary widely, BRIC usually manifests before the second decade of life. There is great variability in terms of frequency (months to years), duration (several days to several months), and intensity of cholestatic episodes. Clinical symptoms may include pruritus, jaundice, fatigue, anorexia, and steatorrhea [Strubbe 2012; Sticova 2018].

During cholestatic episodes, serum bile acids and bilirubin are typically increased, while GGT and serum cholesterol levels are normal [Sticova 2018]. Aminotransferases may be slightly elevated. Liver biopsies have shown hepatocanalicular cholestasis without fibrosis during cholestatic episodes and normal histology during the asymptomatic period.

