Patients/caregivers will be instructed to fill in the electronic diary (eDiary) every morning and evening for the first 24 weeks (Visit 1 through Visit 5) and the 21 days before each clinic visit thereafter (Visit 6 through Visit 12). In addition, Cohort 2 patients/caregivers will be instructed to fill in the eDiary during the screening period. The eDiary will include patient-reported outcome (PRO) and observer-reported outcome (ObsRO) items for evaluation of itching (PRO), scratching (ObsRO), and sleep disturbance (PRO and ObsRO). Observer-reported outcomes in patients of all ages will be recorded by a caregiver. If possible, the same caregiver will complete the ObsRO items throughout the study. Additionally, caregivers will be requested to report in the diary the time that study drug was administered during the Treatment Period.

The patient will return to the clinic after 4 weeks and 12 weeks and thereafter every 10 to 12 weeks for follow-up measurements. Between the clinic visits there will be a telephone contact with the patient/caregiver to report AEs.

The last dose of study drug is taken in the morning the day before Visit 11. If the patient is prematurely withdrawn from the study, all assessments scheduled for Visit 11 will be performed at the time the patient withdraws.

If a liver biopsy is performed according to the local regulations or standard of care at any time during A4250-008, the biopsy results should be recorded in the electronic case report form (eCRF). If the patient had liver biopsy results collected in study A4250-005 or prior to Week 24 in study A4250-008, the patient will be asked to consent to a follow-up liver biopsy, if allowed per local regulations, at Visit 11, unless 2 prior liver biopsy results have been collected with at least 1 year between biopsies. Liver biopsies will not be performed in Spain.

Visit 12 will take place 28 days after Visit 11. All patients prematurely withdrawn will have this visit 28 days after the last dose of study drug for AE and other follow-up.

If a patient discontinues prior to Week 72, additional telephone contacts will be made every 3 months after the Follow-up Visit (Visit 12) up to Week 72 to gather whether or not the patient has had biliary diversion or liver transplantation, and if TEAEs ongoing at the time of discontinuation have resolved. The telephone calls will take place up until 72 weeks even if the patient has biliary diversion or liver transplant.

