9 ASSESSMENT OF EFFICACY

9.1 Efficacy Endpoints

9.1.1 Primary Efficacy Endpoints

The primary efficacy endpoints are:

EU and rest of world: Change from baseline in serum bile acids after 72 weeks of treatment.

US: Proportion of positive pruritus assessments at the patient level over the 72-week treatment period using the Albireo ObsRO instrument.

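### BRIC patients enter in a flare but are assessed with outcomes built for persistent PFIC, so drug effect cannot be separated from the natural end of the episode, and on-study flares are not systematically recorded

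*Protocol*

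**What the plan says.** The Cohort 2 primary objective (Protocol 6.1) is to evaluate the effect of A4250 on bile acids and pruritus, and Cohort 2 includes episodic forms.

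- **Entry (7.2.1, Cohort 2 no. 5).** BRIC patients "must have an emerging flare characterized by clinically significant pruritus and elevated serum bile acid levels/cholestasis as judged by the investigator". The numerical bile acid and scratching thresholds in criteria 3 and 4 do not apply to them.
- **Natural course (5.2.1).** "There is great variability in terms of frequency (months to years), duration (several days to several months), and intensity of cholestatic episodes". Also: "During cholestatic episodes, serum bile acids and bilirubin are typically increased".
- **Outcomes (9.1.1).** For the EU and rest of world: "Change from baseline in serum bile acids after 72 weeks of treatment". For the US: the patient-level proportion of positive pruritus assessments over 72 weeks. Neither has a BRIC version.
- **Baselines and end value (11.2.2.5).** Cohort 2 bile acid baseline is the mean of Visit S-2 and pre-dose Visit 1; the end value is the mean of Weeks 70 and 72. Pruritus baseline is the 14 days before the first dose. A score of 1 or less, or a drop of at least one point, counts as positive.
- **BRIC in the analysis (11.2.2.1).** "Patients with BRIC will be presented separately in efficacy assessments".
- **Flare history (10.2.3).** At Visit S-1, "information on flares will be collected, including frequency, duration, and severity of flares within the last 6 months at a minimum", and up to 5 years where possible.
- **Diary (7.1.1).** Twice daily to Week 24, then only in "the 21 days before each clinic visit thereafter (Visit 6 through Visit 12").

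**The concern.** These patients are selected because an episode is under way, and the result is read about 70 weeks later against a baseline taken around that episode. A patient whose episode simply ends shows a fall in bile acids and a run of positive pruritus assessments, with or without an effective drug. Neither outcome can tell the two apart, and no reference for the natural course is set for BRIC. Elsewhere the protocol does set one: the observational cohort for clinical events (11.1, 11.2.2.6), and the Study A4250-005 placebo patients for bile acids and pruritus (11.2.2.5). Cohort 1, drawn from that study, consists of PFIC Types 1 and 2.

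The natural yardstick in episodic disease is how often flares occur and how long they last. The history needed for that is collected at S-1, but no efficacy endpoint in 9.1 and no method in 11.2.2.5 or 11.2.2.6 uses it. No on-study flare start, stop or count is required. A later analysis plan cannot recover dates that were never recorded.

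**Working it through.** **The plan's own figure.** The protocol gives no figure for BRIC. Its one design figure (11.1: power 89% to 96%, n = 48 to 60) concerns clinical events. It reproduces with an exact binomial calculation (89.8% and 96.6%) and has no bearing here.

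**Step 1. Expected course without drug effect.** The protocol gives only ranges in words, so flare and gap lengths are assumptions. Let flares have mean length D days and flare-free gaps mean G days, both exponential, with every patient in flare on Day 1. The chance of being in flare on day t is

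P(t) = π + (1 − π) · exp(−(1/D + 1/G) · t), with π = D/(D + G).

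By Days 490 and 504 the exponential term is close to zero, so P ≈ D/(D + G):

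- D = 14, G = 730: 14/744 = 2% in flare, 98% out.
- D = 90, G = 180: 90/270 = 33% in flare, 67% out.
- D = 180, G = 180: 180/360 = 50% in flare, 50% out.

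The chance that the entry flare itself is still running at Day 490 is exp(−490/D): below 0.1% for D = 60, 0.4% for D = 90, 6.6% for D = 180.

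**Step 2. Diary days.** Weeks 0-24 give 24 × 7 = 168. The 21-day windows before Visits 6 to 11 (Days 252, 322, 336, 420, 490, 504), with overlaps removed, give 21 + 21 + 14 + 21 + 21 + 14 = 112. Total 280.

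**Step 3. Flare-free share of diary days.** Averaging 1 − P(d) over those 280 days:

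| D | G | Out of flare, Weeks 70-72 | Flare-free diary days |
|---|---|---|---|
| 14 | 730 | 98% | 94% |
| 30 | 365 | 92% | 83% |
| 60 | 365 | 86% | 71% |
| 90 | 180 | 67% | 53% |
| 180 | 180 | 50% | 36% |

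If remission scores are 0 or 1, every flare-free assessment is positive. The last column is then a floor for the positive proportion, since one-point drops during a flare also count. Results go lower when flares outlast the gaps (D = 180, G = 90: 33% and 27%), but that describes near-persistent disease.

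**Step 4. What the diary sees after Week 24.** It covers 112 of 336 days (33%). I enumerated every start day for a flare lying wholly within Days 168-503 and counted flares that touch no diary day:

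- 7 days: 200/330 = 61%
- 14 days: 172/323 = 53%
- 28 days: 116/309 = 38%
- 42 days: 60/295 = 20%
- 60 days: 8/277 = 3%
- over 63 days (the longest gap between windows): none

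Moving the interval by one day changes each figure by less than one percentage point.

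**The case against.** The strongest reply is that the plan is descriptive, has no formal testing, and keeps BRIC out of every pooled summary that includes Cohort 2. A reader might infer that remission will be reported as drug effect. The protocol does not say so and plans no BRIC claim. What remains is that the stated objective is to evaluate effect, and nothing says the BRIC figures cannot show it. Separate presentation protects the pooled summaries, not the BRIC results.

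Other strong readings also go too far:

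- **That these are the only BRIC outcomes.** Sections 9.1.2 and 9.1.3 add bile acids at each visit, pruritus by interval, bilirubin, global impression, sleep and quality of life. The visit series give some view of remission and relapse, but still no reference for the natural course.
- **That the flare history goes unused.** It could appear in the baseline tables by diagnosis (11.2.2.3), and an analysis plan not shown could use it. The point is limited to the protocol's efficacy endpoints and methods, and to on-study flares not being collected.
- **That a large improvement is certain.** It depends on flare and gap lengths and falls to about half or less when flares are long. S-1 is 35 to 56 days before dosing, so a short flare may already be fading at baseline. That shrinks the apparent change without making it interpretable.
- **That later flares are mostly missed.** True only of short ones (Step 4).

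Some flares may surface as adverse events, but not systematically. Sections 10.1.1.1 and 10.1.2 tie an adverse event to worsening from baseline, and a relapse to entry severity arguably is not worsening.

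A historical comparison is itself weak. Only 6 months of history is guaranteed, while episodes may be months to years apart. With the qualifying flare left out, many patients may have no earlier flare in that window, and on-study flares would be captured more fully than past ones. Both tilt the comparison against the drug.

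**Conclusion.** The point stands in limited form. The bile acid change and the positive-assessment proportion cannot answer the Cohort 2 objective for BRIC, because substantial improvement is expected with no drug effect under most assumptions: about 67% to 98% out of flare at Weeks 70-72 and 53% to 94% flare-free diary days, or 50% and 36% in a long-flare case. These figures rest on assumed exponential flare and gap lengths. The conclusion itself rests on what the protocol fixes: entry in flare, baselines taken around it, and an end value at Weeks 70/72. The lack of systematic on-study flare recording is a gap in the protocol that an analysis plan cannot fill. The damage is confined to the BRIC results, for a subgroup whose size is not stated. It merits a change but does not threaten the rest of the trial.

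**What to change.** 1. For BRIC patients, record flare start and stop dates at every existing clinic visit and telephone contact.
2. Make on-study flares per patient-year and days in flare the main BRIC efficacy summary, shown next to the same patient's pre-study history with the qualifying flare left out. State the length of history for each patient, and add a sensitivity summary in those whose history extends well beyond 6 months.
3. State in 11.2.2.1 or 11.2.2.5 that, in BRIC, change from baseline and the positive-assessment proportion are not evidence of drug effect.

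The cost is one eCRF page, one question at contacts that already take place, and a few sentences of endpoint text. The comparison remains descriptive, limited by self-report, by the short guaranteed history, and by fuller capture of flares on study than before it. Those limits should be stated with the results.
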